#### **2.3.1.2 Treated Bleed**

A bleed is considered to be a “treated bleed” if it is directly followed (i.e., there is not an intervening bleed) by a hemophilia medication reported to be a “treatment for bleed,” irrespective of the time between the treatment and the preceding bleed. A bleed and the first treatment thereafter are considered to be pairs (i.e., one treatment belongs to one bleed only), with the following exception: if multiple bleeds occur on the same calendar day, the subsequent treatment is considered to apply for each of these multiple bleeds (which are, however, counted as separate bleeds).

Bleeds due to surgery/procedure are not included in the primary analysis. Only treatments that were recorded as “treatment for bleed” are included in the determination of a treated bleed.

#### **72-Hour Rule**

Two bleeds of the same type (e.g., “joint,” “muscle,” or “other”) and at the same anatomical location are considered to be one bleed if the second occurs within 72 hours from the last treatment for the first bleed. The last treatment is defined as the last treatment before a new bleed occurs, either in the same or in a different location. This is in-line with the above definition that bleeds and treatments are considered to be pairs.

#### **2.3.2 Secondary Efficacy Endpoints**

The same definition of the efficacy period applies to all bleed-related secondary efficacy endpoints.

##### **2.3.2.1 All Bleeds**

“All bleeds” comprises both treated and non-treated bleeds. In this definition, all bleeds are included, irrespective of treatment with coagulation factors, with the following exception: bleeds due to surgery/procedure are excluded as for the primary analysis.

The endpoint of all bleeds fulfills the adapted ISTH criteria, as described in the protocol for the primary endpoint and the 72-hour rule, in particular. For treated bleeds, it is implemented exactly as defined for the primary endpoint. For non-treated bleeds (not followed by any treatments with coagulation factors before the recording of a subsequent bleed), it is implemented by calculating a treatment-free period of 72 hours from the bleed itself.

### **2.3.2.2 Treated Spontaneous Bleeds**

In the analysis of spontaneous bleeds, only treated bleeds that fulfill the 72-hour rule are included.

Bleeds are classified as “spontaneous” if there is no other known contributing factor such as trauma or procedure/surgery.

### **2.3.2.3 Treated Joint Bleeds**

In the analysis of joint bleeds, only treated bleeds that fulfill the 72-hour rule are included. Bleeds due to procedure/surgery are again excluded.

Joint bleeds are defined as bleeds where the bleed type is “joint” as reported in the BMQ and is reported with at least one of the following symptoms: increasing swelling or warmth of the skin over the joint; and/or increasing pain, decreased range of motion, or difficulty using the joint compared with baseline.

### **2.3.2.4 Treated Target Joint Bleeds**

Target joints are joints into which repeated bleeds occur (i.e.,  $\geq 3$  bleeds into the same joint over the last 24 weeks prior to study entry). The target joints prior to study entry are identified through the eCRF. The bleeds in target joints during the efficacy period are defined by first selecting the bleeds that fulfill the definition of a treated joint bleed and then counting how many of these occurred in a target joint as defined prior to study entry. The locations to be taken into account are shoulder, elbow, wrist, fingers/thumb, hip, knee, ankle, sole/heel, and toes. Left and right sides of the same joint type are considered to be separate joints.

### **2.3.2.5 Intra-Patient Comparison**

In the intra-patient comparison (on All Bleeds and on Treated Bleeds as defined in Section 2.3.2.1 and Section 2.3.2.2, respectively), only patients who participated in NIS BH29768 are included. This is because it is possible to apply the detailed bleed definitions only if the data are collected with the same granularity for both time periods. Of note, for some episodic patients who participated in NIS BH29768, the total time in that study prior to enrollment in Study BH30071 may be less than 24 weeks.

The efficacy period in NIS BH29768 is defined as the time from the first entry on the electronic, handheld device or site data entry system to the day the patient completed the study, which may occur between 1 day and a few days prior to

enrollment/randomization in Study BH30071. Usually, the date of the first BMQ entry in NIS BH29768 is the date the Training Module on the electronic, handheld device is completed. The end of the efficacy period in NIS BH29768 is defined as the date of withdrawal or date of study completion or on the day of the clinical cutoff, whichever occurs earlier.

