3. STUDY DESIGN

3.1 DESCRIPTION OF STUDY

This randomized, multicenter, open-label, Phase III clinical study will enroll patients aged 12 years or older with severe hemophilia A (intrinsic FVIII level < 1%) without inhibitors against FVIII. Eighty-five patients who received episodic treatment with FVIII prior to study entry and experience at least 5 bleeds over the prior 24 weeks (ABR \geq 10) will be randomized in a 2:2:1 ratio (see [Figure 1](#)) to the following regimens:

- Emicizumab prophylaxis at 3 mg/kg/wk subcutaneously for 4 weeks, followed by 1.5 mg/kg/wk subcutaneously (Arm A),
- Emicizumab prophylaxis at 3 mg/kg/wk subcutaneously for 4 weeks, followed by 3 mg/kg/2wks subcutaneously (Arm B), or
- No prophylaxis control arm (Arm C).

Randomization will be stratified according to the number of bleeds patients experienced over the last 24 weeks prior to study entry—less than versus greater than or equal to 9 (or ABR 18)—to ensure a balance of patients with lower versus higher number of bleeds in all arms. All patients will use episodic treatment with FVIII at the lowest expected dose to achieve hemostasis in case of a breakthrough bleeding event (see below).

In addition, 40–60 patients with severe hemophilia A who received FVIII prophylaxis prior to study entry will be enrolled and will receive emicizumab prophylaxis at 3 mg/kg/wk subcutaneously for 4 weeks, followed by 1.5 mg/kg/wk subcutaneously (Arm D; see [Figure 1](#)). A minimum of 40 patients in this group will complete at least 24 weeks of observation in an ongoing non-interventional study (BH29768) prior to enrollment in this study. Eligibility for all patients in Arm D will be based on investigator's attestation of adequate prophylaxis regimen in the 24 weeks prior to study entry.

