The reason for the use of FVIII products will be documented (e.g., bleeding, one time prophylaxis, etc.). A thorough documentation of the treatments for bleeds will be required, including agent, start time, dose, route of administration, and number of infusions needed to treat the bleed.

A non-interventional study (BH29768) has been initiated to document the number and types of bleeds and current treatment with episodic or prophylactic FVIII agents, as well as to collect information on HRQoL, health status, and safety in patients with hemophilia A. The assessments in the non-interventional study will mitigate the risk of underreporting of bleeds that likely occurs in the real world, and the resulting data will serve as a source of comparator information for some analyses conducted in the Phase III clinical studies, including this study. In addition, the non-interventional study will enable earlier identification and confirmation of patients who may qualify for the Phase III clinical study. It is anticipated that a significant number of patients participating in Study BH29768 will enroll in this study, as long as they meet the inclusion and exclusion criteria and are able to enroll at a participating site while the study is open for enrollment.

Activity assessment will be conducted at all sites participating in this study, and all patients screened and enrolled will be expected to participate. Participation will not be mandatory and will not impact participation in Study BH30071. Patients will be asked to wear the study device for 2 weeks during Weeks 1–2, 23–24, and 47–48. Patients will return their study devices to the respective site at Weeks 3, 25, and 49 and each site will transfer the data from the device to the database. These data will be analyzed to generate the daily step count (DSC) values for each patient.

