3.3.3 Rationale for Control Group

The control group for the primary efficacy endpoint will be a concurrent, no prophylaxis “usual care” arm, to which patients who were on episodic FVIII prior to study entry will be randomized (2:2:1 prophylactic emicizumab 1.5 mg/kg/wk:prophylactic emicizumab 3 mg/kg/2wks:no prophylaxis), which will enable an inter-patient comparison of the

treatment and control groups. All patients, whether assigned to receive prophylactic emicizumab or no prophylaxis, will continue to receive FVIII on an episodic basis for the treatment of breakthrough bleeds during the study. Specific doses of FVIII will not be mandated in the study, but investigators should review with patients the dose to be used to treat breakthrough bleeds. Breakthrough bleeds should be treated with the lowest FVIII dose expected to achieve hemostasis, which may be lower than the patients' prior FVIII dose.

A second comparison will be an individual patient's bleed rate calculated over the 24 weeks prior to study entry, from the medical record and/or Study BH29768. This will enable intra-patient analyses of bleed rates to be performed.

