4.1.1 Inclusion Criteria

Patients must meet the following criteria for study entry:

- Signed Informed Consent Form by the patient or a legal guardian
- Able to comply with the study protocol, in the investigator's judgment

- Willingness and ability to comply with scheduled visits, treatment plans, laboratory tests, and other study procedures, including the completion of patient-reported outcome questionnaires and bleed and medication diary through the use of an electronic device
- Aged 12 years or older at the time of informed consent
- Body weight ≥ 40 kg at the time of screening
- Diagnosis of severe congenital hemophilia A (intrinsic FVIII level $< 1\%$)
- A negative test for inhibitor (i.e., < 0.6 BU) within 8 weeks of enrollment
- No documented inhibitor (i.e., < 0.6 BU), FVIII half-life < 6 hours, or FVIII recovery $< 66\%$ in the last 5 years
- Patients who completed successful immune tolerance induction (ITI) at least 5 years before screening are eligible, provided they have had no evidence of inhibitor recurrence (permanent or temporary) as may be indicated by detection of an inhibitor, FVIII half-life < 6 hours, or FVIII recovery $< 66\%$ since completing ITI (Antun et al. 2015).
- Documentation of the details of prophylactic or episodic FVIII treatment and of number of bleeding episodes for at least the last 24 weeks
- For patients on no prophylaxis (episodic treatment) pre-study, ≥ 5 bleeds in the last 24 weeks prior to study entry
- Patients who were on FVIII prophylaxis for at least the last 24 weeks, can be enrolled regardless of the number of bleeds during this period. Eligibility will be based on investigator's attestation of adequate prophylaxis regimen.
- At least 40 patients who were on FVIII prophylaxis pre-enrollment will have been enrolled for a minimum of 24 weeks in Study BH29768 (non-interventional)
- Adequate hematologic function, defined as platelet count $\geq 100,000/\mu\text{L}$ and hemoglobin ≥ 8 g/dL (4.97 mmol/L) at the time of screening
- Adequate hepatic function, defined as total bilirubin $\leq 1.5 \times$ the upper limit of normal (ULN) (excluding Gilbert's syndrome) and both AST and ALT $\leq 3 \times$ ULN at the time of screening; no clinical signs or known laboratory/radiographic evidence consistent with cirrhosis
- Adequate renal function, defined as serum creatinine $\leq 2.5 \times$ ULN and creatinine clearance by Cockcroft-Gault formula ≥ 30 mL/min

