6.5.2 Secondary Efficacy Endpoints

For all patients, the number of bleeds over time will be compared with the patient's historical bleed rate, recorded in the medical record, and/or for the duration of their participation in the non-interventional study using an NB regression model similar to the one described for the primary efficacy endpoint.

In addition, the number of all bleeds (treated and not treated), spontaneous, joint and target joint bleeds over 24 weeks' time between the emicizumab prophylaxis and no prophylaxis arms will be evaluated by an NB regression model, as specified for the primary efficacy endpoint.

The efficacy of prophylactic emicizumab treatment in the cohort of non-inhibitor patients previously treated with prophylactic FVIII will be evaluated to demonstrate that these patients remain adequately controlled on emicizumab. The mean ABR will be estimated for each patient using the NB model and the one-sided 97.5% CI constructed around the estimated overall mean ABR. If the upper limit of the CI is less than or equal to 6, the treatment regimen will be considered to provide adequate control. This endpoint will be included as the third test in the hierarchical testing strategy.

Adherence with the HRQoL and health status measures will be summarized at the end of the study.

HRQoL (using the Haem-A-QoL or the Haemo-QoL-SF) and health status (using the EQ-5D-5L) will be assessed on a regular basis, as per the schedule of assessments (scheduled).

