#### **4.5.2 Secondary Efficacy Endpoints**

Type I error for secondary endpoints is controlled through a hierarchical testing framework. The  $\alpha$  level is 0.05. Following the two statistical comparisons described in Section 4.5.1 for the primary endpoint (Arm A versus Arm  $C_{\text{control}}$  and Arm B versus Arm  $C_{\text{control}}$ ) the secondary endpoints are included in the hierarchy in the following order:

- A versus C randomized comparison: all bleeds
- B versus C randomized comparison: all bleeds
- A versus C randomized comparison: treated joint bleeds
- B versus C randomized comparison: treated joint bleeds
- A versus C randomized comparison: treated spontaneous bleeds
- B versus C randomized comparison: treated spontaneous bleeds
- D intra-patient: all bleeds
- D intra-patient: treated bleeds

- A versus C randomized comparison: Haem-A-QoL physical health at 24 weeks
- B versus C randomized comparison: Haem-A-QoL physical health at 24 weeks

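### The Arm D comparator period in SAP 2.3.2.5 does not exclude NIS time before the FVIII prophylaxis on which eligibility rests, which could bias two alpha-controlled tests toward emicizumab

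*SAP*

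**What the plan says.** SAP 2.3.2.5 fixes the comparator period for the intra-patient comparison. On the start: "The efficacy period in NIS BH29768 is defined as the time from the first entry on the electronic, handheld device" or the site data entry system. On the end: "The end of the efficacy period in NIS BH29768 is defined as the date of withdrawal or date of study completion", or the clinical cutoff if that comes first. No maximum length is given, and nothing ties the period to the regimen in use at the time.

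The protocol gives two windows for the same comparison. Section 3.3.3 describes a "bleed rate calculated over the 24 weeks prior to study entry". Section 6.5.2 allows the historical rate to be taken "for the duration of their participation in the non-interventional study". The SAP follows 6.5.2.

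Arm D entry looks back 24 weeks. Protocol 4.1.1 reads: "Patients who were on FVIII prophylaxis for at least the last 24 weeks, can be enrolled regardless of the number of bleeds". Protocol 3.1 bases eligibility on the investigator's "attestation of adequate prophylaxis regimen in the 24 weeks prior to study entry". Protocol 3.1 also says that the NIS documents "current treatment with episodic or prophylactic FVIII agents".

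Two Arm D tests stand in the alpha-controlled list of SAP 4.5.2, beginning with "D intra-patient: all bleeds" and followed by the same comparison for treated bleeds. They are the seventh and eighth secondary tests, ninth and tenth overall after the two primary tests. Two Haem-A-QoL tests come after them.

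**The concern.** The comparison is meant to set emicizumab against adequate FVIII prophylaxis in the same patient. The documents guarantee that regimen only for the last 24 weeks before entry. The 24 NIS weeks required for at least 40 Arm D patients are a minimum, so longer records are allowed. A patient who began prophylaxis during the NIS, and then stayed on it for 24 weeks, is eligible. Under SAP 2.3.2.5 that patient's earlier bleeds and person-time enter the prophylaxis rate.

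The direction follows from the design. The last 24 weeks must be on prophylaxis, so episodic time can only come earlier. Protocol 3.3 treats bleed rates under the two regimens as clearly different, and the case for prophylaxis rests on episodic rates being higher. Such time would raise the comparator rate and make emicizumab look better than it is.

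At stake is a superiority statement against FVIII prophylaxis that carries controlled alpha, and access to the two Haem-A-QoL tests behind it.

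**Working it through.** **1. Does anything else in the plan close the gap?**

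- The NISP population (SAP 4.2.7) labels patients by prior regimen. It does not label periods of time.
- The model (SAP 4.5.2.4) is the primary negative binomial model with a REPEATED statement. No regimen term is described.
- The only Arm D intra-patient sensitivity analysis (SAP 4.5.4) adds time after up-titration. None limits the NIS period by length or regimen.
- SAP 2 and Protocol 3.3 intend at least 40 patients to be observed on prophylaxis in the NIS for at least 24 weeks. This is an enrollment minimum, not an analysis window.

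**2. The plan's nearest figure.** The documents give no power or effect size for the intra-patient tests. The nearest figure is primary power above 90% (SAP 2.4: 30 versus 15 patients, annualized bleed rate (ABR) 4 versus 14, variance 10 times the mean, 0.5 year).

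- Dispersion k = (variance − mean)/mean²: (40 − 4)/16 = 2.25 and (140 − 14)/196 = 0.643.
- SE² = (1/(4 × 0.5) + 2.25)/30 + (1/(14 × 0.5) + 0.643)/15 = 0.0917 + 0.0524 = 0.144, so SE = 0.380.
- Power = Φ(ln 3.5/0.380 − 1.96) = 0.91, as stated.

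**3. Rate ratio with no true effect.** Let p be the ABR on prophylaxis, and also on emicizumab under the null. Let e be the ABR on episodic treatment, T the NIS length in weeks, and s the share of patients whose NIS time before the last 24 weeks was all episodic. None of these four is in the documents for Arm D, so all are assumptions.

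RR = p / [p + (e − p) · s · (T − 24)/T]

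| p, e | T | s = 5% | s = 10% | s = 20% |
|---|---|---|---|---|
| 4, 14 | 36 | 0.96 | 0.92 | 0.86 |
| 4, 14 | 48 | 0.94 | 0.89 | 0.80 |
| 6, 10 | 36 | – | 0.98 | – |
| 6, 10 | 48 | – | 0.97 | – |

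At s = 10% and T = 48: 4/(4 + 10 × 0.10 × 0.5) = 4/4.5 = 0.89, and 6/(6 + 4 × 0.10 × 0.5) = 6/6.2 = 0.97. At s = 0 the ratio is 1 in every case.

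**4. False wins for emicizumab.** Simulation settings: 20,000 trials per cell, 40 patients, T = 48, p = 4, e = 14, dispersion 2.25, and 30 weeks on emicizumab (assumed). The test is the log ratio of mean rates with a paired robust standard error, to which the planned model reduces when follow-up is equal within each period. A false win is z < −1.96, nominally 2.5%. Patient frailty was either fully shared between the two periods or independent.

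| Frailty | s = 0 | 5% | 10% | 20% |
|---|---|---|---|---|
| Shared | 3.7% | 7.4% | 13.1% | 30.4% |
| Independent | 3.9% | 4.9% | 7.0% | 11.0% |

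The excess over 2.5% at s = 0 is small-sample error of the robust standard error. With e = 10 instead of 14, the s = 10% figures fall to 9.6% (shared) and 5.6% (independent).

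**5. With the comparator limited to the last 24 weeks.** Across 40 to 60 patients and dispersion 1 to 2.25 (assumed frailty correlation 0.7, 0.65 year on emicizumab), the simulated null ratio is 0.99–1.00 and false wins are 2.7–4.1%.

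**The case against.** The strongest reply is that the harm is hypothetical. No passage reports an Arm D patient who changed regimen during the NIS, or how long any NIS record ran beyond 24 weeks. SAP 2 and Protocol 3.3 plainly intend NIS time on prophylaxis, so other time would be the exception. How the NIS itself handles regimen changes cannot be seen from these documents. All of this stands. A reader might infer that the two tests are in fact tilted, but the documents do not support that.

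A reader might also infer that the SAP departs from the protocol. It does not: it follows the protocol's statistical section, 6.5.2. The conflict is inside the protocol, with the rationale in 3.3.3, and the SAP carries it forward without comment.

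The illustrative rates are open to challenge too. The plan assumes ABR 4 for emicizumab, and 14 for randomized controls selected for at least 5 bleeds in 24 weeks. Neither is a figure for FVIII prophylaxis or for patients who later moved to it. Treating all excess weeks as episodic is also near the worst case. If half are, the 48-week ratio at s = 10% is 4/(4 + 10 × 0.10 × 0.25) = 0.94.

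Finally, the randomized bleed comparisons come earlier in the hierarchy and are untouched. What remains is a derivation rule that does not enforce the comparator that the design intends.

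**Conclusion.** The concern holds in conditional form. The stated period does not exclude NIS time before the qualifying prophylaxis, and any episodic time there would count as FVIII prophylaxis in two alpha-controlled tests. If episodic rates are higher, as the design supposes, the bias would favour emicizumab.

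Its size depends on inputs that the documents do not give. It is zero if no Arm D patient had such time. With 10% of patients affected, a 48-week NIS and all excess time episodic, the null ratio lies between about 0.89 (ABR 4 and 14) and 0.97 (6 and 10). With 4 and 14, false wins are roughly 7–13%, against about 4% with no such time. The larger simulated figures, up to 30%, need 20% of patients affected and fully shared frailty, and should not be read as expected values.

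The rule is worth changing because the correction is cheap. The inconsistency between Protocol 3.3.3 and 6.5.2 needs settling even if nobody changed regimen.

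**What to change.** - In SAP 2.3.2.5, start the Arm D NIS comparator period at the later of (a) the first NIS bleed and medication questionnaire entry and (b) the start of the continuous FVIII prophylaxis that supports eligibility, taken from NIS medication records.
- In SAP 4.5.4, add a sensitivity analysis limited to the last 24 weeks before entry, the window in Protocol 3.3.3. Keeping this as a sensitivity analysis avoids discarding longer valid time on prophylaxis from the main analysis.
- Report the distribution of NIS duration and the number and timing of regimen changes among Arm D patients.
- Reconcile Protocol 3.3.3, Protocol 6.5.2 and SAP 2.3.2.5 so that they name one window.

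The cost is one derivation from medication data that the NIS already collects, some SAP wording, and a small loss of comparator person-time in patients who changed regimen. Patients on prophylaxis throughout the NIS are unaffected. The pooled Arm A and B intra-patient comparison is outside the hierarchy (SAP 4.5.2.6) and needs no matching change for this purpose.

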#### **2.3.2.6 Haem-A-QoL at 24 Weeks**

The Haem-A-QoL and the Haemo-QoL-SF will be used to measure HRQoL in adults and adolescents, respectively. Therefore, all calculations and analyses will be conducted separately for these two measures. Total score and physical health subscale score for the Haem-A-QoL will be evaluated at 24 weeks in the study and formally analyzed as described in the efficacy analysis section. However, only the physical health subscale will be part of the hierarchical testing procedure highlighted in this analysis section. Other subscale scores will be analyzed in a descriptive way.

The number of adolescent patients in the randomized portion of the study will be too small to provide meaningful statistical analyses of the Haemo-QoL-SF and therefore the analysis of this endpoint will be descriptive.

